## **10.3. Subject Withdrawal Criteria**

### **10.3.1. Early Withdrawal from the Study**

Patients must remain in the study until the last scheduled visit at Month 2 (Visit T3) to be considered as having completed participation in the study.

Patients who temporarily withdraw from IMP prior to Month 2 (Visit T3) for any reason may restart IMP providing that 1) the patient and the investigator are in agreement regarding this course of action, 2) the patient has been off of IMP for 2 weeks or less; and 3) IMP can be started as soon as possible. For cases where the patient has been off of IMP for more than 4 weeks, the investigator must contact the medical monitor for approval prior to restarting IMP.

The patient's decision to participate in the clinical study is voluntary. Patients may refuse to continue in the study and/or withdraw from participation in this study at any time, for any reason, specified or unspecified, and without penalty or loss of benefits to which the patient is otherwise entitled.

It is the right and duty of the Investigator to interrupt the treatment of any patient whose health or well-being may be threatened by continuation in this study. Such patients should be withdrawn from the study and should not be continued under a modified regimen.

Patients who are withdrawn from the study may not re-enter. The reasons for withdrawal from this study may include:

- Patient's withdrawal of consent
- Failure to comply with the protocol
- Lost to follow-up
- Illness, condition, or procedural complication (including AEs) affecting the patient's ability to participate or requiring prohibited medication
- The Sponsor or Investigator terminates the study
- In the Investigator's judgment, it is deemed in the best interest of the patient to discontinue his/her participation in the study
- Any other reason

If a patient is lost to follow-up, every reasonable effort must be made by the clinical site personnel to contact the patient and determine the reason for discontinuation/withdrawal. The measures taken to follow-up must be documented.

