### **8.3. Blinding**

Patients who satisfy all entry criteria during the screening phase and complete the PCSK9i run-in period will be randomized to a treatment group at Day 1 (Visit T1). The Investigator or designee will contact IWRS at this visit to randomize the patient into the study. The IWRS will determine the randomized treatment assignment number and the appropriate study drug container via medication identification numbers (MED ID). A patient is considered to be randomized when they have been assigned a MED ID number by IWRS.

After patients have been randomized, study drug, which is assigned by the IWRS, will be administered in a double-blind fashion. The Sponsor, all clinical site personnel (Investigator, pharmacist, etc), and other vendor personnel will be blinded to the treatment group for each patient. Patients will also be blinded to the treatment they receive. Unblinded User(s) will be designated for each clinical site and at the sponsor (or designee) as needed. Unblinded individuals will be provided IWRS access allowing them the ability to perform emergency unblinding of treatment for an individual patient. An affirmative entry of the user's login details will be required before the treatment group is displayed. Unblinding at the clinical site for any other reason will be considered a protocol deviation. Unblinded treatments for patients will NOT automatically discontinue the patient from the study. To discontinue the patient from the study, the appropriate clinical site personnel will need to register the 'discontinuation' visit separately.

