#### 10.2.6. Treatment Month 1 (Visit T2 $\pm 3$ days)

If the patient is withdrawing early from the study at this visit, proceed to [Section 10.3.2](#) for the list of the required assessments.

If the patient is withdrawing from IMP treatment at this visit, proceed to [Section 10.3.2](#) for the list of the required assessments.

Patients will undergo the following assessments and procedures at Month 1 (Visit T2):

- Concomitant and prohibited medication review (ongoing)
- Assess AEs since last visit (ongoing)
- Vital signs
- Clinical laboratory evaluations:
  - Hematology, blood chemistry, and urinalysis

- Basic fasting lipids (TC, calculated LDL-C, [REDACTED], non-HDL-C, [REDACTED], and [REDACTED])
- ApoB and hs-CRP
- Predose PK. Should be taken ideally within 4 hours of the patient's normal time of dosing
- Conduct diet and exercise counseling
- Return of IMP; assessment and recording of IMP compliance
- Dispense IMP and provide dosing instructions (35-day supply bottles)
- PCSK9i injection and IMP must be given at the end of procedures
- Schedule next visit

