### **10.3.2. Procedures for Early Withdrawal**

If a patient withdraws or is removed from the study for any reason, all End of Study procedures should be completed. Reason for withdrawal, date of the discontinuation, and date of the last dose of study drug should be recorded in the appropriate section of the eCRF. Additionally, the discontinuation visit date must be registered in IWRS. Study drug assigned to the withdrawn patient may not be assigned to another patient.

All effort should be made to have each patient complete all study visits on schedule according to the protocol. Accommodations for early or late visits in special circumstances will be considered by the Sponsor to prevent early withdrawal. Written notice (regardless of cause) is to be provided within 48 hours of the withdrawal to the Sponsor personnel or the Medical Monitor. At the time of discontinuation, every effort should be made to ensure all relevant procedures and evaluations scheduled for the final study visit are performed. Except in the case of a medical emergency, the procedures and assessments detailed in [Section 10.2.7](#) will be performed upon the discontinuation of the study.

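### Section 10.3.1 takes safety-interrupted patients out of the study, the laboratory sections and the Appendix 1 note keep them in, and the restart rule skips 15 to 28 days off drug

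*Protocol*

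**What the plan says.** **Study withdrawal.** Protocol 10.3.1 gives the investigator the duty to interrupt treatment in any patient whose health may be threatened by continuing. It adds: "Such patients should be withdrawn from the study and should not be continued under a modified regimen". It also says: "Patients who are withdrawn from the study may not re-enter".

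**Stopping or holding IMP.**
- 11.1.5.4.1 (liver tests), 11.1.5.4.2 (creatinine/eGFR) and 11.1.5.4.3 (creatine kinase, CK) take patients off IMP and ask them to remain on the visit schedule for safety.
- The liver section also allows interruption and rechallenge. The CK section allows a hold and possible resumption.
- The Appendix 1 note, repeated in the SAP's Appendix 1, keeps consenting off-drug patients on schedule, in clinic or by phone.

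**Procedures.** At Month 1, 10.2.6 states "If the patient is withdrawing from IMP treatment at this visit, proceed to" 10.3.2, and 10.2.7 does the same at Month 2. Section 10.3.2 describes only leaving the study: "If a patient withdraws or is removed from the study for any reason, all End of Study procedures should be completed". It also requires the discontinuation visit to be registered in IWRS. Section 8.3 says of that registration: "To discontinue the patient from the study, the appropriate clinical site personnel will need to register the 'discontinuation' visit separately".

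**Restart.** Under 10.3.1, patients who pause IMP temporarily, whatever the reason, "may restart IMP providing that 1) the patient and the investigator are in agreement regarding this course of action". A second condition is that "the patient has been off of IMP for 2 weeks or less". The section then says: "For cases where the patient has been off of IMP for more than 4 weeks, the investigator must contact the medical monitor for approval".

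**The concern.** Two sets of instructions apply to the same patient. A confirmed large transaminase rise, acute renal failure or a symptomatic CK rise is naturally a threat to health, so 10.3.1 removes that patient from the study for good. The laboratory sections take the same patient off drug only, and some of their tiers foresee a return to drug. That cannot happen after a withdrawal with no re-entry. Section 10.3.1 also sits badly with itself, because its restart paragraph applies whatever the reason for the pause.

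Three things depend on the section a site follows:
- whether the remaining scheduled safety laboratories and lipids are collected;
- whether the patient counts as withdrawn from the study or only from study drug, which SAP 5.2.4 tabulates separately;
- when general SAE reporting ends under 12.2.2.

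The restart rule is a separate defect: a 20-day gap has no stated route, while a 30-day gap has one.

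**Working it through.** **1. The passages side by side**

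| Question | 10.3.1 / 10.3.2 | 11.1.5.4.1–3 and Appendix 1 note |
|---|---|---|
| What stops after a safety interruption? | Study participation | IMP |
| Can the patient return to IMP? | No re-entry after study withdrawal | Yes, in some liver and CK tiers |
| Are later visits held? | One End of Study assessment | Yes, on schedule, by request and consent |
| IWRS discontinuation registered? | Yes | Not stated for an IMP-only stop |

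Section 11.1.5.4 introduces the laboratory sections as specific guidance, but nothing says they override 10.3.1. Two bullets speak of withdrawing the patient without saying from what: the first liver bullet and the one for CK above 10 × ULN. The Appendix 1 note makes a Visit T4 the exit visit for patients who decline follow-up, yet the schedule ends at T3/EOS. The cross-reference to 10.3.2 matters at T2, since T3 is already the last visit.

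**2. Consequence in days (illustrative)**

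Inputs: T2 is Day 31 and T3 is Day 61, each ±3 days (Appendix 1). General SAE reporting runs to 30 days after study completion or discontinuation (12.2.2). AE collection runs to 30 days after the last dose of study treatment (12.1.3). Assumptions: study withdrawal falls on the day *s* that IMP stops, and the patient would have consented to off-drug follow-up.

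- Kept to T3: SAE reporting ends on 61 + 30 = Day 91. With the T3 window, 58 + 30 = 88 to 64 + 30 = 94.
- Withdrawn on day *s*: it ends on *s* + 30.
- Difference: 91 − (*s* + 30) = 61 − *s*.

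| Stop day *s* | End if withdrawn | End if kept | Difference (days) | Scheduled visits still due |
|---|---|---|---|---|
| 1 | 31 | 91 | 60 | 2 (T2, T3) |
| 15 | 45 | 91 | 46 | 2 (T2, T3) |
| 31 (at T2) | 61 | 91 | 30 | 1 (T3) |
| 60 | 90 | 91 | 1 | 1 (T3) |

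If the last dose of study treatment is also on day *s*, AE collection ends on *s* + 30 under both readings (Day 45 for *s* = 15, Day 61 for *s* = 31). SAEs considered related to IMP remain reportable after the 30 days. The difference is therefore chiefly new SAEs not considered related to IMP.

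**3. Restart rule**

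Two weeks or less is up to 14 days, and more than four weeks is 29 days or more. Gaps of 15 to 28 days, that is 28 − 15 + 1 = 14 gap lengths, meet neither sentence. Such a gap fits within the treatment period of Day 1 to Day 61. The only recourse is the general contact for unavoidable protocol departures in 18.2.

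**The case against.** The 10.3.1 sentence could be a residual power for patients endangered by remaining in the study at all, with the named laboratory rules governing their own cases. That is workable, but it is not written: the trigger is any patient and the action is interruption of treatment. Health interruptions outside the liver, renal and CK rules have no specific section to fall back on.

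On IWRS, 10.2.6 sends IMP-only stops to 10.3.2 for assessments, and footnote 12 of Appendix 1 ties the contact to study discontinuation. This suggests that an IMP-only stop is not registered, without saying so. The Appendix 1 note already lists the off-drug assessments, so what is missing is a statement that it prevails over 10.3.1.

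On size, post-dose safety laboratories are scheduled only at T2 and T3, and the liver and CK rules want a repeat test, preferably 3 to 7 days after the result. From scheduled samples, the earliest confirmed stop under those rules is about Day 28 + 3 = Day 31, leaving one visit and at most about 61 − 31 = 30 days. This is right for those rules. The 46- and 60-day figures need an unscheduled laboratory test or a non-laboratory stop, which 10.3.1 and the Appendix 1 note also cover.

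Finally, the silence on 15 to 28 days may be a deliberate bar. If so, it is odd that a longer gap has an approval route, and the text should say what is meant.

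**Conclusion.** The inconsistency is real in the current text, in both parts. For a consenting patient with a safety interruption, the reading chosen changes one or two scheduled visits, the disposition category, and the end of general SAE reporting by 61 − *s* days: 46 for a Day 15 stop, 30 for a Day 31 stop, and between 60 and 1 over Days 1 to 60. These figures assume withdrawal on the stop day. For a patient who declines off-drug follow-up there is little difference.

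The loss is limited. Section 10.3.2 requires End of Study procedures and asks that visits be completed on schedule. Section 12.1.6 requires repeat assessments, until resolution or stabilization, for AEs that force study discontinuation. The documents do not allow the number of affected patients to be derived, and no effect on the primary estimate is claimed.

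**What to change.** - Reconcile 10.3.1 with 10.2.6, 10.2.7, 10.3.2, 11.1.5.4.1 to 11.1.5.4.3 and the Appendix 1 note, keeping stopping or interrupting IMP distinct from leaving the study throughout, including in the two unclear bullets.
- Add one statement of which passage governs and which scheduled safety laboratories and lipids continue for consenting patients.
- State whether the IWRS discontinuation registration applies to an IMP-only stop.
- Correct the Visit T4 reference in the protocol and in the SAP copy.
- Reconcile the two restart sentences so that the text says what applies at every gap length, whether or not restart is allowed.

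The clinical rule and the thresholds are for the sponsor's medical lead to settle. The cost is a wording clarification in the protocol and a corrected note in the SAP appendix. It needs no visits beyond those already scheduled.

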### **10.3.2. Procedures for Early Withdrawal**

If a patient withdraws or is removed from the study for any reason, all End of Study procedures should be completed. Reason for withdrawal, date of the discontinuation, and date of the last dose of study drug should be recorded in the appropriate section of the eCRF. Additionally, the discontinuation visit date must be registered in IWRS. Study drug assigned to the withdrawn patient may not be assigned to another patient.

All effort should be made to have each patient complete all study visits on schedule according to the protocol. Accommodations for early or late visits in special circumstances will be considered by the Sponsor to prevent early withdrawal. Written notice (regardless of cause) is to be provided within 48 hours of the withdrawal to the Sponsor personnel or the Medical Monitor. At the time of discontinuation, every effort should be made to ensure all relevant procedures and evaluations scheduled for the final study visit are performed. Except in the case of a medical emergency, the procedures and assessments detailed in [Section 10.2.7](#) will be performed upon the discontinuation of the study.

## **11. ASSESSMENT OF SAFETY**

### **11.1. Safety Parameters**

At all clinic visits, investigators will review all safety information including vital signs, AEs, and concomitant medications and will ensure that the collected data are recorded into the appropriate eCRF. Additionally, clinical laboratory samples will be collected and sent for analysis and the investigator will review the results to ensure continued patient safety while participating in the study.

#### **11.1.1. Demographic/Medical History**

Demographic data and a complete medical history will be obtained from the patient. For medical history, conditions that are relevant and/or clinically significant should be captured with at least a start date (month and year) and whether the condition is ongoing or resolved. All surgeries regardless of date should be reported.

#### **11.1.2. Vital Signs**

Vital signs will include DBP and SBP as well as heart rate.

The patient should sit quietly for 5 minutes prior to collection of vital signs. At all time points, vitals will be collected prior to blood collection. Blood pressure (BP) and heart rate will be measured using a calibrated, fully automated machine with a cuff that is appropriate to the size of the upper arm. If a fully automated machine is not available, BP may be measured manually. The same method (either automated or manual) and the same arm (right or left) must be used throughout the study. The patient should be in a seated position with feet touching the floor. Patients should be seated quietly for at least 5 minutes in a chair with their backs supported, their feet flat on the ground, and their arms bared and supported at heart level.

#### **11.1.3. Weight, Height, and Body Mass Index**

Weight will be measured on a calibrated scale while fasted and after voiding. Body weight will be measured while fasting, using consistent scales, after voiding, and without shoes and outerwear (eg, coats).

Height will be measured using standard clinic procedures.

BMI will be calculated using the formula:

$$\text{BMI (kg/m}^2\text{)} = \text{weight in kg} / (\text{height in meters})^2$$

#### **11.1.4. Physical Examination**

PEs will include an assessment of the following:

- General appearance
- Skin
- Eyes, ears, nose, and throat
- Head and neck
- Extremities
- Musculoskeletal examination
- Respiratory examination
- Cardiovascular assessment, including rhythm and presence of cardiac abnormalities
- Abdominal examination
- Neurologic examination including documentation of the presence of abnormalities in mental status and motor and sensory function
- Any additional assessments necessary to establish baseline status or evaluate symptoms or adverse experiences

Documentation of the PE findings will be included in the source documentation at the clinical site. Significant findings prior to the time of ICF signature will be recorded on the Medical History/Current Medical Conditions page of the eCRF. Only changes from baseline PE findings that meet the definition of an AE will be recorded on the AE page of the eCRF.

Note: Additional information will be collected regarding muscle-related AEs. See [Section 12.3](#).

#### **11.1.5. Clinical Laboratory Tests**

##### **11.1.5.1. Laboratory Parameters (Safety)**

Patients will be in a seated position during the blood collection. Clinical laboratory parameters and tests will include those listed in [Table 3](#). Collection schedule, schedule of laboratory parameters by visit, and instructions are in the Clinical Laboratory Manual provided by Central Laboratory.

**Table 3: Clinical Laboratory Parameters (Safety)**

Clinical Laboratory Test	Clinical Laboratory Test

Hematology
 
 
• Hematocrit (Hct)
 
• Hemoglobin (Hgb)
 
• Mean corpuscular hemoglobin (MCH)
 
• Mean corpuscular hemoglobin concentration (MCHC)
 
• Mean corpuscular volume (MCV)
 
• Platelet count
 
• Red blood (RBC) cell count
 
• White blood (WBC) cell count with differential (absolute and %)
 
	
Blood Chemistry (serum, fasting)
 
 
• Albumin (Alb)
 
• Alkaline phosphatase (ALK-P)
 
• Alanine aminotransferase (ALT; SGPT)
 
• Aspartate aminotransferase (AST; SGOT)
 
• Blood urea nitrogen (BUN)
 
• Calcium (Ca)
 
• Carbon dioxide (CO2)
 
• Chloride (Cl)
 
• Creatinine
 
• Creatine kinase (CK)
 
• Glucose
 
• Lactate dehydrogenase (LDH)
 
• Phosphorus
 
• Potassium (K)
 
• Sodium (Na)
 
• Total and direct bilirubin (TB)a
 
• Total protein
 
• Uric acid
 

Urinalysis (Dipstick)
 
 
• Clarity
 
• Bilirubin
 
• Color
 
• Glucose
 
• Ketones
 
• Leukocyte esterase
 
• Nitrate
 
• Occult blood
 
• pH
 
• Protein
 
• Specific gravity
 
• Urobilinogen
 
	
Coagulation—only in patients receiving anticoagulant therapy that in the investigator's judgment require monitoring at T1 and 3 to 5 days post-T1
 
 
• Prothrombin time (PT)
 
• International normalized ration (INR)
 

Urinalysis (Microscopic)-only if urine dipstick abnormal
 
 
• Bacteria
 
• Casts
 
• Crystals
 
• Epithelial cells
 
• Red blood cell (RBC)
 
• WBC
 
	
Additional samples
 
 
• Hemoglobin A1C (HbA1C)
 
• PK
 

**Table 3: Clinical Laboratory Parameters (Safety)**

Clinical Laboratory Test	Clinical Laboratory Test
Other Screening Labs 

• Hepatitis B surface antigen (HBsAg), hepatitis C virus (HCV)b

• Serum pregnancy test (only for females of childbearing potential)

• Follicle-stimulating hormone (FSH; Females <55 years and >1 year without menses)

• Urine pregnancy test prior to randomization (for female of child bearing potential)

• Thyroid-stimulating hormone (TSH)

	

a If TB  $\geq 1.2 \times$  ULN, a reflex indirect (unconjugated) bilirubin will be obtained.

b If HCV-AB is positive, a reflex HCV RNA will be performed to rule out active disease.

#### **11.1.5.2. Clinical Laboratory Tests (PK)**

Trough PK plasma concentrations of bempedoic acid and its metabolite ESP15228 will be collected prior to dosing at Visits T1, T2, and T3. See lab manual for additional details.

Patients will be in a seated position during the blood collection. Collection schedule and instructions are provided in the Clinical Laboratory Manual. A description of the sample collection, storage, and shipping are described in Section 11.1.5.3.

#### **11.1.5.3. Sample Collection, Storage, and Shipping**

Clinical laboratory samples will be collected by appropriate clinical site personnel and then shipped according to a separate laboratory manual provided by the Central Laboratory. Samples will be processed by the Central Laboratory, and PK samples will be forwarded to the Bioanalytical Laboratory for analysis.

Blood draws for lipids, [REDACTED], and glucose must meet the criteria listed below. If these criteria have not been met, these blood samples will NOT be collected. If these criteria can be met by rescheduling the clinic visit to occur within 3 days, the lipid, [REDACTED], and/or glucose blood samples will be collected at the rescheduled clinic visit only.

- Blood samples will be drawn after a minimum 10-hour fast (water is allowed)

#### **11.1.5.4. General Monitoring and Management of Abnormal Clinical Labs**

It is the Investigator's responsibility to review the results of all laboratory tests as they become available and to sign and date the report to document their review. For each laboratory test outside of the laboratory normal range, the Investigator needs to ascertain if this is a clinically significant change from baseline for the individual patient. The Investigator may repeat the laboratory test or request additional tests to verify the results of the original laboratory test.

If a laboratory value is determined to be an abnormal and clinically significant change from baseline for the patient, the Investigator should determine if it qualifies as an AE, and if yes, an appropriate eCRF will be completed. All clinically significant laboratory abnormalities occurring during the study that were not present at baseline should be followed and evaluated with additional tests if necessary, until diagnosis of the underlying cause or resolution. Specific monitoring and management guidelines for laboratories of special interest are outlined in the sections below.

#### **11.1.5.4.1. Monitoring and Management of Elevated Liver Function Tests**

If at any time after randomization a patient experiences a new ALT and/or AST  $>3 \times$  ULN, the patient will undergo repeat confirmatory liver function test (LFT) assessment as soon as is reasonably possible, preferably within 3 to 7 days of the laboratory result becoming available.

Repeat LFT assessment will include: 1) measurement of ALT, AST, alkaline phosphatase, total and direct bilirubin, prothrombin time (PT)/international normalized ratio (INR), eosinophil count, CK, antihepatitis A virus (total), HBsAg (confirmation of screening measurement), HCV (confirmation of screening measurement), and anticytomegalovirus/immunoglobulin M; 2) history of concomitant medication use; 3) history of exposure to environmental chemical agents, including ethanol; and 4) query for related symptoms. Additionally, further testing such as liver ultrasound or magnetic resonance imaging (MRI) scanning may be warranted to rule out additional pathology depending on clinical presentation and should be discussed with the Sponsor personnel or the authorized Medical Monitor.

- If repeat LFT assessment confirms ALT and/or AST  $>3 \times$  ULN, consideration should be given to withdrawing the patient and administering no further doses of study drug. At the investigator's discretion, study drug may be interrupted and the patient rechallenged with study drug after LFTs have returned to baseline levels.
- If repeat LFT assessment confirms ALT and/or AST  $>5 \times$  ULN, patient should be withdrawn from IMP treatment, but will be asked to continue to be followed for safety using the protocol-specified visit schedule (see [Appendix 1](#)).
- If repeat LFT assessment confirms ALT and/or AST  $>3 \times$  ULN in addition to any of the following, the patient should be given no further IMP treatment, but will be asked to continue to be followed for safety using the protocol-specified visit schedule (see [Appendix 1](#)):
  - TB  $>2 \times$  ULN  
Note: In the case of patients with Gilbert's disease, TB will be fractionated and the determination of  $2 \times$  ULN will be based upon direct (conjugated) bilirubin.
  - INR  $>1.5 \times$  ULN (unless the patient is on stable dose of anticoagulation medication)
  - Appearance or worsening of right upper abdominal discomfort, anorexia, fatigue, nausea, vomiting, fever, rash, or eosinophilia

